## Withdrawal criteria

Upon inclusion (i.e. Visit 1) we screen for:

- 1) Biliary obstruction – plasma total bilirubin must be  $< 2 \times$  upper normal limit
  - 2) Pregnancy – plasma/urine HCG must be negative in all women of childbearing potential
- The screening result must be available before randomisation (i.e. at Visit 2).

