## Study subjects

### **Inclusion criteria**

- Patients referred to Clinical Physiological/Nuclear Medicine departments for SeHCAT at Holbæk, Hvidovre, Aarhus, and Aalborg University Hospitals
- Suspected BAD
- $\geq 18$  and  $< 80$  years of age.
- Women of fertile age must use safe contraception during the treatment part of the study
  - spiral or hormonal contraception, ie. birth control pill, hormonal implant, transdermal patch, vaginal ring, or contraceptive depot injection.
  - Sexual abstinence from heterosexual intercourse. May be accepted as safe contraception by the investigator in a case by case assessment a
  - Vasectomised partner
- Ability to give informed consent after written and oral information in the Danish language

Note a) sexual abstinence from heterosexual intercourse is deemed a highly effective method of anticonception by the Clinical Trials Facilitation Group. It is accepted in this trial only because the duration is short – three weeks.

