**Study visit 2 – Assessment of eligibility by stool diary results**

**Study Day 8.** Concurrent with the second SeHCAT visit, all subjects meet in the fasting state, the only exception is drinking still water. Subjects must not ingest alcohol on the day before visit 2.

Fasting blood samples are drawn from all subjects, no later than 10:00 AM.

The blood samples include: 4mL plasma for C4 and for FGF19 analysis (total 8mL). Routine samples for: p-triglycerides, p-cholesterols (total, High and Low-Density Lipoproteins), fasting p-glucose.

Any violation of alcohol abstinence the day before study visit 2 and of pausing statin/fibrate use leads to exclusion as a protocol violation. Minor violations of fasting (drinking thin fluids like coffee or tea, also with milk added) are noted in the CRF and the patient can participate in the study. All other violations lead to exclusion or rescheduling for fasting blood sampling another day.

The (sub)investigator collects the baseline study diary and tallies this.

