**Subjects with diarrhoea:**

This is the ITT population.

Adverse Event registration starts now (study day 8) and includes all subjects with diarrhoea.

The (sub)investigator dispatches the relevant double blinded treatment packet according to the randomisation sequence.

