**Start of intervention and possibility for delay of intervention**

If the time/hour of the day for visit 2 enables the subject to take two doses of the medication this day, the intervention may start on visit 2, which subtracts one day from the time schedule below.

For logistic reasons in the collaboration between the Department of Nuclear Medicine and the Department of Gastroenterology at the local study centre, the treatment start may be delayed for a maximum of seven days. In case the start is postponed, the postponed days are not counted as study days.

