**Telephone consultation: Start of intervention****Study day 10**

The intervention has started on study day 9. The study nurse calls the subject to note possible early AEs, aid compliance, and to titrate the dose. If the nurse suspects an SAE, she contacts the investigator.

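### In the visible text the qualifying hCG test is 7–8 days old at first dose (14–15 at maximum delay), and the contraception criterion as worded does not cover that interval

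*Combined protocol and SAP*

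**What the plan says.** Pregnancy is listed under Exclusion criteria, and the Ethics section repeats that pregnant women are excluded. Withdrawal criteria sets the check at inclusion, identified there as Visit 1: "Pregnancy – plasma/urine HCG must be negative in all women of childbearing potential". It adds: "The screening result must be available before randomisation (i.e. at Visit 2"). The second sentence fixes when the result must be known, not when the sample is taken, so a negative sample from Visit 1 satisfies it.

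At Visit 2 (study day 8) the blood list covers C4 and FGF19 and continues: "Routine samples for: p-triglycerides, p-cholesterols (total, High and Low-Density Lipoproteins), fasting p-glucose". For subjects with diarrhoea, "The (sub)investigator dispatches the relevant double blinded treatment packet according to the randomisation sequence". On timing of the first dose, the telephone consultation section for study day 10 says "The intervention has started on study day 9". The section on start and delay of intervention allows a start at Visit 2 itself. It also says that for logistic reasons "the treatment start may be delayed for a maximum of seven days", and those days are not counted as study days. No repeat hCG is named at Visit 2, at a postponed start, at either telephone call or at Visit 3.

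On contraception, Inclusion criteria says: "Women of fertile age must use safe contraception during the treatment part of the study". Note a, on abstinence as a method, says: "It is accepted in this trial only because the duration is short – three weeks". The Design section gives 12 days of blinded treatment.

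**The concern.** The plan chose to exclude pregnancy and to enforce that with a test. The test is tied to study entry, while exposure begins at least a week later. The usual bridge over such an interval is a contraception requirement, but this one is worded for treatment, which starts where the interval ends. As written, a woman could meet every criterion, conceive around or after Visit 1, and be dosed without the plan detecting it. What is at stake is participant safety and the clarity of the eligibility rule, not the trial's inference.

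**Working it through.** The documents give no figure for the test-to-dose interval, so there is none to reproduce. One check on the calendar is possible: treatment on days 9–20 is 20 − 9 + 1 = 12 days, which agrees with the Design section.

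**Inputs**
- Visit 1, and the hCG test: day 1 (Study visit 1; Withdrawal criteria).
- Visit 2: day 8 (Study visit 2).
- First dose: day 9 by default, or day 8 if started at Visit 2.
- Maximum postponement: 7 calendar days. The text does not say whether it runs from day 8 or day 9, so both are shown.
- Treatment length: 12 days (Design).
- Three weeks in note a: 21 days.

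**Formulas**, in calendar days from Visit 1 = day 1
- Gap now = first dose − 1.
- Gap with a test at Visit 2 = first dose − 8.
- Last treatment day = first dose + 11. Counted inclusively from Visit 1, this is also the length of the period needing contraception.

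| Schedule | First dose | Gap now | Gap with Visit 2 test | Visit 1 to last treatment day | Against 21 days |
|---|---|---|---|---|---|
| Start at Visit 2 | 8 | 8 − 1 = 7 | 8 − 8 = 0 | 8 + 11 = 19 | −2 |
| Default | 9 | 9 − 1 = 8 | 9 − 8 = 1 | 9 + 11 = 20 | −1 |
| Maximum delay from day 8 | 8 + 7 = 15 | 15 − 1 = 14 | 15 − 8 = 7 | 15 + 11 = 26 | +5 |
| Maximum delay from day 9 | 9 + 7 = 16 | 16 − 1 = 15 | 16 − 8 = 8 | 16 + 11 = 27 | +6 |

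**Reading the table**
- The usual schedule gives 7 or 8 days. The 14–15 days arise only if the full postponement is used.
- The contraception criterion as worded covers 12 days, none of which lie in the gap.
- Note a's three weeks matches the 19–20 days of an undelayed schedule far better than the 12 treatment days, so the sponsor probably meant the longer period. It falls 5–6 days short at maximum delay.
- A Visit 2 test alone leaves 7–8 days at maximum delay, about the same as today's usual gap. There the contraception rule has to do the rest.

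**Sensitivity.** If the 24-hour reflection time in Information and consent moves inclusion and the test to day 2, the range becomes 8 − 2 = 6 to 16 − 2 = 14 days. Rescheduled fasting sampling at Visit 2 could lengthen it. Neither changes the conclusion.

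**The case against.** The strongest objection is that the absence of a repeat test cannot be established. The Appendix 1 study overview chart is not shown and is a natural place to schedule one. The text's sample lists are also incomplete: the Visit 1 baseline bloods omit the hCG that Withdrawal criteria requires, so silence at Visit 2 is weak evidence. This stands, and it is why the testing part of the fix is conditional. It does not reach the contraception part, which concerns wording that is visible.

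Second, a negative hCG is already required before randomisation. A reader might infer that women enter treatment unchecked; the documents do not support that. The question is only how recent the test is, and the documents set no standard that 7–8 days would breach.

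Third, most accepted methods (intrauterine or hormonal contraception, a vasectomised partner) are continuing ones, so many women would be protected from Visit 1 anyway. That is largely right. It is weaker for abstinence, and for anyone who begins a method just for treatment. A reader might also infer that the sponsor deliberately limited contraception to the 12 treatment days. The criterion does not say so, and note a points the other way.

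Fourth, a reader might infer that one cheap test at Visit 2 closes the gap completely. It does not: 7–8 days remain at maximum delay, and a test on day 8 may miss a very recent conception. Bringing the gap to zero after a delay needs a test on the start day, and the visible text describes no in-person contact then.

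**Conclusion.** The point holds as a low-severity safety and wording improvement. In the visible text the qualifying test precedes first dose by 7–8 days in the usual schedule and by 14–15 days at maximum delay, and neither the test nor the contraception criterion, as worded, covers that interval.

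Expected harm is small. The protocol describes colesevelam as unabsorbed (End of the clinical study phase), treatment lasts 12 days, and with 1:1 allocation about half of any affected women would receive placebo. The documents do not give the number of women affected or how often starts are postponed; the number may be close to zero. A reader might take 15 days as typical or infer a threat to the results. The first is the extreme of a permitted exception, and the second has no basis, since the primary analysis and power are untouched.

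The conclusion assumes that the hCG is sampled at Visit 1 as stated and that the unseen chart adds no later test. If the chart does schedule one at Visit 2, only the contraception wording remains to be corrected.

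**What to change.** 1. **Inclusion criteria.** Require safe contraception from Visit 1 to the last treatment day, including any postponed days. Adjust note a so that its duration also covers a postponed start (26–27 days at most).
2. **Withdrawal criteria and Study visit 2.** Do or repeat the urine hCG, which the plan already permits, at Visit 2 before the treatment packet is dispatched, unless Appendix 1 already schedules this. A positive result is then a screen failure before allocation.
3. **Optional.** Retest on the day of a postponed start. This brings the gap to 0 days but needs an extra contact or a home kit, so it need not be mandatory once the first change is in place.

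The cost of the first two is a few lines of text and one inexpensive urine test, for women of childbearing potential, at a visit every subject already attends. The downside is a rare late screen failure. Sample size, analysis and power do not change.

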## Endpoints

### Primary endpoint

Placebo-controlled ITT diarrhoea remission rate defined by the Hjortswang criteria for colesevelam in patients with BAD defined by  $C4 > 46$  ng/mL.

**Handling of missing data:** drop-outs are set as treatment failures in the ITT analysis if less than five of the last seven treatment days that comprise the endpoint assessment period are complete. If five or more of these days are complete, a mean of these days will be used for calculating the Hjortswang response criterium.

**Statistical analysis:** data will be longitudinally correlated (baseline, run-in, endpoint assessment period for each patient) and nested within study sites. Thus, data will not be independent and cannot correctly be assessed with simple statistical tests. Therefore, we will fit an appropriate generalized linear mixed-effects model with an unstructured covariance pattern of the chance of response with colesevelam versus placebo. In addition, baseline adjustments for the severity of

diarrhoea (mean per day sum of Bristol type 6 and 7 stools) and the severity of bile acid malabsorption (visit 2 C4 value) will be made to avoid skewed randomisation of these prognostic covariates by chance (40). This baseline adjustment is clinically relevant as, in the future, diarrhoea severity and C4 should be available for physicians before starting therapy.

The model fit will be assessed by inspection of scaled residual plots and QQ-plots.

**Sensitivity analyses:** The robustness of the statistical modelling of the primary endpoint will be addressed in sensitivity analyses of different approaches.

Different handling of missing values: 1) any missing diary day of the last seven treatment days and the patient treatment is set to failure; 2) excluding patients who drop out due to large pill size (the DB caps used for trial blinding are significantly larger than the colesevelam tablet), 3) using multiple imputations for missing values.

Strict Hjortswang's response criteria: no watery stools (Bristol stool type 6 or 7) during the last seven treatment days.

Different C4 cut-off used to define bile acid diarrhoea: C4 > 25 ng/mL; C4 > 58 ng/mL.

If possible, given that the study is not powered for stratification, we will assess remission rates in stratification intervals defined by C4 0–25 ng/mL, >25–46 ng/mL.

Different statistical modelling and assessment: 1) added adjustment for patient sex and age, 2) model without baseline adjustment, 3) model without random effect of study site, 4) a simple Fisher's exact test of a 2x2 table (response versus treatment allocation) reporting remission rates.

## Secondary endpoints

### 1. PP analysis for the primary endpoint

Statistical analysis: this is an efficacy (*de jure*) estimand for colesevelam. Modelling as for the primary endpoint but with imputation of missing data as if all patients had adhered (41, 42). This includes all patients with bile acid diarrhoea and complies with a *per protocol* principle.

### 2. Placebo-controlled diarrhoea ITT remission rate for colesevelam defined by the Hjortswang criteria in patients with BAD defined by SeHCAT $\leq 10\%$

Statistical analysis: as the primary endpoint but with baseline adjustment for SeHCAT, not C4.

Sensitivity analyses: as for the primary endpoint. Instead of differing C4 cutoffs, the SeHCAT cutoffs  $\leq 5\%$ , and  $\leq 15\%$  will be assessed.

### 3. Placebo-controlled diarrhoea PP remission rate for colesevelam defined by the Hjortswang criteria in patients with BAD defined by SeHCAT $\leq 10\%$

Statistical analysis: this is an efficacy (*de jure*) estimand for colesevelam. Modelling as for the primary endpoint with baseline adjustment for SeHCAT and with imputation of missing data as if all patients had adhered.

#### 4. Placebo-controlled effect of colesevelam in all treated patients

Statistical analysis: as for the primary endpoint but instead of the binary Hjortswang response criteria as outcome, continuous variables will be modelled with suiting baseline adjustment:

- a. the absolute number of stools (mean per day over 6 or 7 days)
- b. the total number of Bristol 6 and 7 stools (mean per day over 6 or 7 days)

#### 5. The *de facto* effectiveness of colesevelam on health related quality of life assessed as the sum of Short Health Scale scores.

Statistical analysis: modelling with adjustment for baseline SHS score

The secondary endpoints are tested with correction for multiple statistical testing and significant results are reported as such.

The secondary endpoints will also be tested at the 0.05 significance level and reported as hypothesis-generating results acknowledging the risk of type 1 error.

### Expected missing data and drop-outs

We anticipate dropout/missingness due to

1) side effects to colesevelam. We presume this to be 'missing at random'.

Drop-out from this cause could dilute the observed effect of colesevelam. This reflects real-world effect and is accounted for by analysing both an effectiveness (ITT) and an efficacy (PP) estimand.

2) lack of effect from placebo. Presumably somewhat dependent on baseline diarrhoea severity, which is controlled for in the modelling.

Drop-out from this cause probably has no effect on the primary endpoint.

3) due to the (large) pill size. We presume this will be 'missing at random'.

Drop-out from this risks diluting the observed effect of colesevelam. This is only specific to the trial context and not future clinical practise. We take this into account in a sensitivity analysis excluding these cases.

## Statistical analysis plan for ancillary endpoints

### Diagnostic validation endpoints

- Placebo-controlled diarrhoea ITT remission rate for colesevelam defined by the Hjortswang criteria in patients with BAD defined by fasting FGF19  $\leq 60$  pg/mL
- ROC analyses to assess the negative predictive values of C4  $< 15$  ng/mL, FGF19  $> 204$  pg/mL, SeHCAT  $> 10\%$ , respectively with diarrhoea remission defined by Hjortswang criteria as gold standard test.
- Repeatability of baseline fasting C4 and FGF19 assessed with marginal limits of agreements (Bland-Altman plot) comparing visit 2 samples with 'optimal' visit 1 samples (ie. fulfilling

visit 2 sampling criteria: fasting, not using statins within a week, no alcohol consumption within 24h)

- Exploratory assessment of the effect of sampling time, statin use, and alcohol intake on C4. This is a regression model of C4 at visit 2 explained by: C4 at visit 1, sampling time, alcohol consumption, statin use, respectively.
- ROC-AUC for all visit 1 C4 samples versus SeHCAT  $\leq 10\%$  as gold standard
- Placebo-controlled subjectively assessed "good response" ITT rate in the primary endpoint population
- Diagnostic values for subjectively assessed "good response" in the colesevelam-arm
  - C4 > 46 ng/mL
  - SeHCAT  $\leq 10\%$

## Descriptive statistical analyses

- correlations between each of FGF19, C4, and SeHCAT and baseline mean stools and number of watery stools
- correlations between each of FGF19, C4, and SeHCAT and change in mean stool number and number of watery stools in the colesevelam population

## Exploratory analyses of bile acid species in plasma and feces

We will explore the distribution of bile acid species in feces and plasma regarding bile acid diarrhoea both defined with C4 and SeHCAT. Exploratory statistical modeling will be done to analyse the diagnostic and prognostic performance of bile acid parameters. Bile acid species will primarily be assessed as sums of primary and secondary species given as a percentage of the total amount of bile acids. Percentages of the total amount of bile acids have less variability than absolute amounts (43). Secondary analyses of single bile acid species and conjugation forms either on absolute values or percentages may be performed given a relevant signal in the primary exploratory analysis.

## Elucidation of further aspects of treatment effect

- Placebo-controlled ITT diarrhoea remission rate defined by the Hjortswang criteria for colesevelam in patients with BAD by C4  $\geq 46$  ng/mL AND
  - fecal primary bile acids >10%, and >15%
- Logistic regression model predicting remission in the colesevelam group for
  - C4 controlled for baseline mean stools/day
    - Sensitivity, specificity, PPV and NPV for C4 > 46 ng/mL
      - Model characteristics reported with mean stools/day
  - SeHCAT controlled for baseline mean stools/day
    - Sensitivity, specificity, PPV and NPV for SeHCAT  $\leq 10\%$

- Six-month follow up on the aetiology of diarrhoea
- Six -month follow up on medication
- Exploratory regression analyses to determine if fecal or plasma bile acid profile may be a predictor for diagnosis and for treatment response.
- Placebo-controlled change in fecal bile acids during treatment with colesevelam.

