## Summary of expected improvements from the study

The present diagnosis of BAD rests on the radionucleotide based SeHCAT test that has limited accessibility. Patients with BAD therefore often endure an extensive diagnostic workup including endoscopies before referral for SeHCAT. Consequently, the patients are often misdiagnosed and suffer impaired quality of life although treatment for BAD exists. A biochemical test will allow timely screening of patients with chronic diarrhoea in analogy with tests for celiac disease, increase awareness of BAD, reduce diagnostic delay, and the exposure to unnecessary invasive examinations. Demonstrating the treatment effect of colestevlam in a randomised placebo-controlled trial and correlating each biochemical test result with the subsequent treatment effect will improve both the diagnostic strategy and the treatment of BAD considerably. This crucial link between test and expected treatment effect is currently missing and providing this will help doctors treat and advise their patients better.

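### Test accuracy for C4 and SeHCAT is planned in the colesevelam arm only, benefit in test-negatives is conditional, and no treatment-by-marker contrast is named, so the promised link between test and treatment effect is only partly estimated

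*Combined protocol and SAP*

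**What the plan says.** Aim 2 is to correlate SeHCAT and C4 with response to colesevelam and to validate the cut-offs from the earlier validation study. The Summary of expected improvements goes further. It speaks of correlating test results with treatment effect and states: "This crucial link between test and expected treatment effect is currently missing". The Ethics section expects that a blood test alone may come to make the diagnosis.

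The relevant analyses are:

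- **Placebo-controlled, test-positives.** Remission for C4 >46 ng/mL, with >25 and >58 as sensitivity cut-offs (Primary endpoint); SeHCAT ≤10%, with ≤5% and ≤15% (secondary endpoints 2 and 3); FGF19 ≤60 pg/mL, and subjective good response as an "ITT rate in the primary endpoint population" (Diagnostic validation endpoints); C4 combined with faecal primary bile acids (Elucidation of further aspects of treatment effect).
- **Placebo-controlled, all treated patients.** Secondary endpoint 4, on two continuous stool outcomes, not split by marker.
- **C4-negatives.** The Primary endpoint section says: "If possible, given that the study is not powered for stratification, we will assess remission rates in stratification intervals defined by C4" 0–25 and >25–46 ng/mL.
- **SeHCAT-negatives.** Secondary endpoint 2 says: "Sensitivity analyses: as for the primary endpoint. Instead of differing C4 cutoffs, the SeHCAT cutoffs" ≤5% and ≤15% are used. No SeHCAT >10% group is named.
- **Colesevelam patients only.** Sensitivity, specificity, PPV and NPV for remission ("Logistic regression model predicting remission in the colesevelam group for" C4 and SeHCAT); the item beginning "Diagnostic values for subjectively assessed" good response; and correlations of each marker with "change in mean stool number and number of watery stools in the colesevelam population".
- **No arm named.** "ROC analyses to assess the negative predictive values of C4", FGF19 and SeHCAT against remission.

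Within the efficacy models C4 and SeHCAT appear only as baseline adjustment.

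**The concern.** A treatment effect is a difference between colesevelam and placebo. For a test to guide treatment, that difference must be known on both sides of the cut-off. Accuracy measured in the treated arm counts every remission as response, including remission that would also have occurred on placebo; the plan itself assumes 27% placebo remission in bile acid diarrhoea. Such figures describe who remits while on the drug. They cannot show whether patients below the cut-off also gain from it, which is what a reader will want to know if the test is to stand alone. The one planned analysis that would show this directly for C4, the by-stratum remission rates, is left conditional, and whether it carries over to SeHCAT >10% is unclear. If the plan is not firmed up beforehand, the decision that stratification was or was not possible may be taken with results in hand.

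**Working it through.** **1. The plan's own sample size.** For 67% v 27%, two-sided 0.05 and 80% power, the pooled two-proportion formula gives 24 per arm against the stated 23; power at 23 per arm is 79.6%. Then 46/0.27 = 170.4, against 170 stated. So 170 randomised patients means about 23 test-positive and (170 − 46)/2 = 62 test-negative per arm by C4.

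**2. Colesevelam-arm accuracy does not identify benefit.** The documents give no remission rates for test-negatives, so those below are assumptions. Let 23 test-positives remit at 67% and 62 test-negatives at 40% on colesevelam:

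- sensitivity = 23×0.67/(23×0.67 + 62×0.40) = 38%
- specificity = 62×0.60/(62×0.60 + 23×0.33) = 83%
- PPV = 67%, NPV = 60%

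No placebo quantity enters these formulas. They stay the same while the benefit in test-negatives varies:

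| Placebo remission, test-negatives | Benefit, test-negatives | Benefit in positives (40 points) minus benefit in negatives |
|---|---|---|
| 40% | 0 points | 40 points |
| 27% | 13 | 27 |
| 17% | 23 | 17 |
| 7% | 33 | 7 |

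With 27% remission on colesevelam in test-negatives the figures are sensitivity 48%, specificity 86%, PPV 67%, NPV 73%. Over 10–35%, sensitivity runs from 71% to 42% and NPV from 90% to 65%. The non-identification holds for any values.

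**3. Stratum sizes.** Table 1 has 25 patients with SeHCAT ≤10% and 34 with SeHCAT >10%. From its sensitivities and specificities:

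- C4 >25: 0.72×25 = 18, plus 0.18×34 ≈ 6, gives 24/59
- C4 >46: 0.52×25 = 13, plus 0.09×34 ≈ 3, gives 16/59, as in the Power calculation
- hence >25–46 is 8/59 and 0–25 is 35/59

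Scaled to 170 patients these are about 46, 23 and 101.

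**4. Precision.** The 95% CI half-width for colesevelam minus placebo is 1.96×√(p₁q₁/n + p₀q₀/n). Test-negative groups are set at an assumed 27% v 27%, the primary population at 67% v 27%.

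| Group | n per arm | Half-width, points |
|---|---|---|
| C4 0–25 | 50 | 17 |
| C4 >25–46 | 11–12 | 36–37 |
| All C4 ≤46 | 62 | 16 |
| SeHCAT >10% (34/59) | 49–50 | 17–18 |
| Primary population, C4 >46 | 23 | 26 |

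Table 1's printed PPVs do not match these counts: 18/24 = 75% against 64% printed for C4 >25, and 13/16 = 81% against 72% for C4 >46. Taking 64% instead gives 18/0.64 ≈ 28/59 above 25. The 0–25 stratum then falls to about 45 per arm (±18 points) and the middle stratum rises to about 17 per arm (±30). Alternatively, the text above Table 1 counts 13/59 above 46; that gives about 19 per arm above 46 (±29) and 16 per arm in the middle stratum (±31), with 0–25 unchanged.

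**5. Power of a C4 interaction at 170 patients**, dichotomised at 46, unadjusted, two-sided 0.05, placebo remission 27% throughout:

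| Gain in test-negatives | Risk-difference scale | Log-odds scale |
|---|---|---|
| 0 points | contrast 0.40, SE 0.157: 72% | 1.70, SE 0.762: 61% |
| 10 points | 0.30, SE 0.158: 47% | 1.24, SE 0.754: 38% |
| 20 points | 0.20, SE 0.159: 24% | 0.83, SE 0.751: 20% |

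The contrast has a CI half-width of about 31 points. With 19 and 66 per arm, power is 67%/55% for no gain and 43%/34% for a 10-point gain.

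For a continuous log-C4 interaction, 3,000 simulated trials per scenario gave 45% (no gain) and 26% (10-point gain) if benefit steps at 46 ng/mL, and 82% and 54% if it rises smoothly with log C4. Those simulations used a two-lognormal C4 distribution built from the Table 1 medians and IQRs, and no covariates. SeHCAT could not be simulated because no distribution is given.

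**The case against.** The yardstick is rationale text. Aim 2 asks for correlation with response to colesevelam, and analysing the treated arm is the direct way to provide it; the regression is openly labelled as predicting remission in that arm. No listed endpoint promises a treatment-by-marker estimate. Much of the test-negative information is also planned. The C4 strata belong to the sensitivity analyses of a placebo-controlled endpoint, so comparison by arm is their natural reading, and together with the primary population they cover the whole C4 range. SeHCAT strata are arguably inherited, and secondary endpoint 4 covers all treated patients. Leaving a weakly powered interaction unnamed is defensible in a trial sized for 46 marker-positive patients. Finally, the stratum sizes rest on Table 1 counts that do not agree with its PPVs.

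Much of this stands. Aim 2's literal wording is met, the interaction has low to moderate power, and the missing ROC arm is a matter of detail. It does not remove the gap. The trial presents itself as supplying the link to treatment effect, and treated-arm accuracy cannot do so at any sample size. The power caution fits the >25–46 stratum but not 0–25, which on any reading of Table 1 is estimated more precisely than the primary population.

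**Conclusion.** The concern holds. The plan firmly estimates benefit over placebo in test-positives, but benefit in test-negatives only conditionally for C4 and unclearly for SeHCAT, and it names no contrast between the two. The accuracy figures are valid as prediction of remission on treatment and uninformative about drug benefit below the cut-off. The precision figures rest on the Table 1 distribution applying to 170 patients and on assumed remission rates in test-negatives. The non-identification rests on neither. This is a worthwhile improvement to ancillary analyses, of minor to moderate weight; the primary and secondary conclusions do not depend on it.

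**What to change.** 1. Make the C4 strata in the Primary endpoint section unconditional. Report remission by arm and the colesevelam-minus-placebo difference with its CI above and below each cut-off, flag >25–46 ng/mL as imprecise, and state the SeHCAT >10% counterpart under secondary endpoint 2.
2. Add one exploratory model per marker in all randomised patients: remission on treatment, the marker (log C4, or SeHCAT), treatment × marker, baseline stools and site.
3. Name the arm for the ROC and negative-predictive-value analysis. Keep the colesevelam-arm accuracy figures, described as prediction of remission on treatment.

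The cost is SAP wording and a little analysis, since all data are already collected. The drawback is the limited interaction power. Both the strata and the model are therefore wanted, conclusions should rest on estimates and CIs, and a non-significant interaction should not be read as rejecting the test.
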